8.7.5 Method of Detecting AEs and SAEs

Care will be taken not to introduce bias when detecting AEs and/or SAEs. Open-ended and non-leading verbal questioning of the participant is the preferred method to inquire about AE occurrences.

8.7.6 Recording and Follow-Up of AE and/or SAE

8.7.6.1 AE and SAE Recording

When an AE/SAE occurs, it is the responsibility of the investigator to review all documentation (e.g., hospital progress notes, laboratory reports, and diagnostics reports) related to the event.

- The investigator will then record all relevant AE/SAE information.
- It is **not** acceptable for the investigator to send photocopies of the participant's medical records in lieu of completion of the required form.
- There may be instances when copies of medical records for certain cases are requested by the sponsor, RA, or EC. In this case, all participant identifiers, with the exception of the participant number, will be redacted on the copies of the medical records before submission.
- The investigator will attempt to establish a diagnosis of the event based on signs, symptoms, and/or other clinical information. Whenever possible, the diagnosis (not the individual signs/symptoms) will be documented as the AE/SAE.

8.7.6.2 Assessment of Severity

The investigator will assess severity for each AE and SAE reported during the study and assign it to one of the following categories:

- **Mild:** No limitation in normal daily activity.
- **Moderate:** Some limitation in normal daily activity.
- **Severe:** Unable to perform normal daily activity.

8.7.6.3 Assessment of Causality

The investigator is obligated to assess the relationship between study intervention and each occurrence of each AE/SAE. The relationship of study treatment to an AE will be determined by the investigator based on the following definitions:

1. "Not Related": The AE is not related if exposure to the investigational product has not occurred, or the occurrence of the AE is not reasonably related in time, or the AE is considered unlikely to be related to use of the investigational product, i.e., there are no facts, evidence, or arguments to suggest a causal relationship, or the AE is more likely related to the subject's pre-existing condition.

2. “Related”: The administration of the investigational product and AE are considered reasonably related in time and the investigational product is more likely than other causes to be responsible for the AE or is the most likely cause of the AE. A reasonable possibility of a relationship conveys that there are facts, evidence, and/or arguments to suggest a causal relationship, rather than a relationship cannot be ruled out.

The causality assessment is one of the criteria used when determining regulatory reporting requirements.

- Alternative causes, such as underlying disease(s), concomitant therapy, and other risk factors, as well as the temporal relationship of the event to study intervention administration, will be considered and investigated.
- The investigator will also consult the IB and/or product information, for marketed products, in their assessment.
- For each AE/SAE, the investigator **must** document in the medical notes that they have reviewed the AE/SAE and has provided an assessment of causality.
- Following an initial report, the investigator may change their opinion of causality in light of follow-up information and send an SAE follow-up report with the updated causality assessment.

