3.0 Objectives and Endpoints

The overall objective of this pharmacokinetic study is to assesses the effect of food on the relative bioavailability of MDMA in healthy volunteers.

Table 2: Objectives and Endpoints

Objectives	Endpoints
Primary	
To evaluate the effect of a high fat (high calorie) meal as compared to administration in the fasted state on the relative bioavailability of oral MDMA capsules in healthy volunteers.	PK parameters determined for MDMA and its active metabolite MDA: area under the concentration-time curve from dosing time to last measurement time (AUC_{0-t}), area under the concentration-time curve from dosing time to infinity ($AUC_{0-\infty}$), and peak concentrations (C_{max}).
Safety	
To characterize the cardiac-related effects of MDMA by collecting supportive ECG data.	Mean change from baseline QT interval corrected for heart rate.
To observe the rates of treatment emergent adverse events of special interest that would reflect a serious arrhythmia or suggest the potential for such an arrhythmia.	The rates of the following events: 
 • Torsade de pointes (TdP) • Sudden death • Ventricular tachycardia • Ventricular fibrillation and flutter • Syncope of cardiovascular etiology
To evaluate the effect of MDMA and its active metabolite MDA, on hemodynamic parameters compared to baseline when administered to healthy volunteers.	Change from baseline in basal (resting) hemodynamic parameters: heart rate (HR) systolic blood pressure (SBP), diastolic blood pressure (DBP).

To further evaluate the safety and tolerability of MDMA in both fed and fasted states.	Incidence of adverse events, clinical laboratory test results, and vital sign measurements (body temperature).
Exploratory	
To further characterize the subjective effects of MDMA.	Change in subjective effects (self-reported VAS) from pre-dose to multiple timepoints post-dose.

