9.3.3 Safety Analyses

Safety and tolerability will be evaluated. Safety analyses include change from Baseline blood pressure, pulse, and temperature values at specified time points. All laboratory results and vital sign measurements will be summarized using appropriate descriptive statistics.

Adverse event (AE) data will be descriptively evaluated. Descriptive statistics (e.g., number of observations, means, standard deviations, medians, maximum and minimum values) will be used to summarize continuous variables. Frequencies, proportions, and the exact 95% confidence intervals (CI), when appropriate, will be used to summarize categorical variables. Subject listings will also be provided.

Suicidal ideation and behavior will be summarized according to suggestions made in the C-SSRS Scoring and Data Analysis Guide. The number and percent of positive responses of Positive Ideation, Serious Ideation, and Positive Behavior will be tabulated by treatment group and time period (lifetime, screening, baseline, each Dosing Session (pre- and post-IMP), Integrative Sessions, and endpoints). Frequency and incidence of positive or serious ideation and suicidal behavior will be presented using descriptive statistics in tabular format.

ECG analysis: Mean of the triplicate ECGs at each nominal time point will be used for all reporting and analysis; however, individual values will be used to calculate the correction coefficient (γ) for the individual correction QTc (QTcI). Individual correction coefficient, γ , will be estimated using linear regression of log QT on log RR for each subject using all baseline ECG assessments collected before Day 1 dosing within a subject.

The QTc corrections will be individual correction by QTcI = QT/RR^γ , Fridericia's by QTcF = $QT/RR^{0.33}$, and Bazett's by QTcB = $QT/RR^{0.5}$.

Change from baseline ($\Delta QTcI$) will be calculated as the average of the three predose assessments on Day 1 subtracted from the value (i.e., QTc) on Day 1 at a given time t . The effect of MDMA on cardiac repolarization will be assessed, as measured by the time point with the largest upper one-sided 95% confidence limit for the $\Delta QTcI$. The relationship between $\Delta QTcI$ (dependent variable) and MDMA or MDA concentrations (independent variable) will be determined using a linear mixed-effects model.

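### The two causality categories rest on two different thresholds and leave some adverse events without a category

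*Protocol*

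**What the plan says.** All of the following is in Protocol section 8.7.6.3 unless another section is named.

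- **Related, first sentence.** The timing of the AE must fit the dosing. A further condition concerns likelihood: "the investigational product is more likely than other causes to be responsible for the AE or is the most likely cause of the AE".
- **Related, second sentence.** "A reasonable possibility of a relationship conveys that there are facts, evidence, and/or arguments to suggest a causal relationship". The sentence ends by separating this from a relationship that merely cannot be excluded. It does not say how it bears on the first sentence.
- **Not Related.** Any one of four conditions is enough: no exposure; no reasonable time relation; the AE is considered unlikely to be related, which the text explains with an 'i.e.' as "there are no facts, evidence, or arguments to suggest a causal relationship". The fourth condition names one competing cause: "the AE is more likely related to the subject's pre-existing condition".
- **What the investigator must weigh.** "Alternative causes, such as underlying disease(s), concomitant therapy, and other risk factors", as well as timing. This list is wider than the single competing cause named under Not Related.
- **Use.** "The causality assessment is one of the criteria used when determining regulatory reporting requirements".

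On analysis, section 9.3.3 states that "Adverse event (AE) data will be descriptively evaluated". The tolerability endpoint in Table 2 (section 3.0) is the incidence of AEs, with no restriction to related ones.

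**The concern.** A two-category rule works only if every event falls into exactly one category and one test decides which. Here the Related definition contains a test that ranks MDMA against other causes and a description that does not. Not Related is not written as the complement of either.

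This trial makes the gap more than theoretical. Participants are judged generally healthy at entry (section 5.1), so the one competing cause that Not Related names should seldom apply. The protocol itself introduces other candidate causes: an overnight fast of at least 10 hours (5.3.1), no caffeine for at least 12 hours and no nicotine from 7 days before the first session (5.3.2), and a high-fat meal of about 800 to 1000 calories in the fed session (8.3.2). Nausea after the meal and headache after caffeine abstinence are plausible examples.

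What is at stake is whether the causality call means the same thing from one event and assessor to the next. That matters for any summary of related AEs and for reporting decisions. For example, section 8.7.4 makes notification of an SAE learned of after discharge depend on the investigator finding it reasonably related.

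**Working it through.** No figure is involved, so the check is a listing of cases. Take an exposed participant whose AE is reasonably related in time. This removes the first two routes to Not Related. Then cross whether evidence points to MDMA with how likely MDMA is compared with other causes.

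| Case | Evidence for MDMA? | Relative likelihood | Comparative test in Related | Reasonable-possibility description | Not Related | Result on a literal reading |
|---|---|---|---|---|---|---|
| 1 | Yes | MDMA most likely; a competing cause is less likely | Met | Met | Not met | Related |
| 2 | Yes | MDMA and another cause equally likely | Not met | Met | Not met | No category |
| 3 | Yes | A cause other than a pre-existing condition is more likely | Not met | Met | Not met | No category |
| 4 | Yes | A pre-existing condition is more likely | Not met | Met | Met | Not Related |
| 5 | No | Any | – | Not met | Met | Not Related |

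Case 2 fails the comparative test because MDMA is neither more likely than the alternative nor the single most likely cause. It is not Not Related either: there is supporting evidence, and no pre-existing condition is more likely.

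Case 3 depends on the 'i.e.' explanation. Read literally, unlikely means that no supporting evidence exists, so an event with such evidence cannot be called unlikely. The alternative may be concomitant therapy, or the protocol's meal, fast or caffeine and nicotine abstinence. None of these is a pre-existing condition, so the last route to Not Related is closed as well. If unlikely is read loosely, as ordinary judgement, case 3 can go to Not Related.

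Two defects follow.

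1. **The categories are not exhaustive.** Case 2 has no category, and neither does case 3 on the literal reading.
2. **The thresholds conflict.** In cases 2, 3 and 4 the comparative test fails while the reasonable-possibility description is met. Case 4 is assigned to Not Related although it meets that description.

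The direction of miscoding depends on which sentence a site follows. If it follows the first and defaults to Not Related, cases 2 and 3 are under-coded relative to the reasonable-possibility standard. If it follows the second, they become Related. The protocol gives no AE count and no share of events with competing causes, so the number affected cannot be derived.

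**The case against.** The strongest reply is that the second sentence of Related is not a rival threshold. Its ending excludes relationships that merely cannot be ruled out, so it may only explain what evidence is needed before the comparison is made. Unlikely can also be read as everyday investigator judgement, which closes case 3. Both readings are possible, but the text states neither, and case 2 stays open under both.

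The reply is right to limit the consequences. A reader might infer more than the protocol supports:

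- **That every AE with a plausible competing cause falls between the categories.** It does not. Case 1 is Related and case 4 is Not Related.
- **That Related means a probability above one half.** The text also accepts the most likely cause. MDMA at 40% against two other causes at 30% each would be Related.
- **That related AEs are under-counted.** This is conditional on how sites resolve the conflict; the text supports inconsistency with that risk.
- **That the fed-versus-fasted tolerability comparison is distorted.** The stated endpoint is AE incidence regardless of cause, the AE analysis is descriptive, and no comparison of related AEs is named. The overnight fast, the bar on food for 4 hours after dosing and the caffeine and nicotine limits apply to both sessions; only the meal differs.
- **That serious events will go unreported.** SAEs during the study reach the sponsor within 24 hours whatever their causality (8.7.4, 8.7.8), causality is only one reporting criterion, and the investigator may revise it. The cardiac and suicide-related events of special interest are defined by event, not by causality (8.7.3).

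**Conclusion.** The point holds as a defect in the definition. Section 8.7.6.3 mixes two thresholds within Related and does not give every event a category. The uncovered events are those with evidence for MDMA and either an equally likely other cause or, if the 'i.e.' explanation is taken literally, a more likely cause that is not a pre-existing condition.

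The consequence is inconsistent coding, with a risk of under-coding as related. It reaches any tabulation of related AEs and the investigator's causality call used in regulatory reporting. It does not reach the AE-incidence endpoint. Its size cannot be computed from the protocol.

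The statistical analysis plan is not at hand, so whether it tabulates related AEs is unknown. It could not repair the problem in any case, because the investigator makes the call during the trial under the protocol's wording.

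**What to change.** Amend section 8.7.6.3 and the CRF completion guidance as follows.

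1. Define Related by one threshold: reasonably related in time, with a reasonable possibility of a causal relationship. That means evidence or argument in favour of one, and not just an inability to exclude it.
2. Delete the test that MDMA be likelier than other causes or the likeliest cause.
3. Define Not Related as every case that does not meet the Related definition.
4. State how an event is classified when an alternative cause is more likely but there is also evidence for MDMA, both for a pre-existing condition and for any other cause (concomitant therapy, meal, fast, caffeine or nicotine abstinence). If the sponsor wants a more likely pre-existing condition to remain Not Related, write it as an explicit exception. Limiting that clause to events without evidence for MDMA would add nothing, since those are already Not Related.

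The cost is about two sentences of protocol text and matching site guidance. The downside is that the count of related AEs may look slightly less favourable. The change should be in place before sites code events, so that all are judged by one rule.

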8.7.6.4 Further Evaluation of AEs and SAEs

The investigator is obligated to perform or arrange for the conduct of supplemental measurements and/or evaluations as medically indicated or as requested by the sponsor to elucidate the nature and/or causality of the AE or SAE as fully as possible. This may include additional laboratory tests or investigations, histopathological examinations, or consultation with other health care professionals.

- If a participant dies during participation in the study or during a recognized follow-up period, the investigator will provide the sponsor with a copy of any postmortem findings including histopathology.
- New or updated information will be recorded in the originally submitted documents.
- The investigator will submit any updated SAE data to the sponsor within 24 hours of receipt of the information.

After the initial AE/SAE report, the investigator is required to proactively follow each participant at subsequent visits/contacts. All SAEs and AESIs will be followed until resolution, stabilization, the event is otherwise explained, or the participant is lost to follow-up, as defined in [Section 7.3 Lost to Follow-up](#).

8.7.7 Reporting of SAEs

8.7.7.1 SAE Reporting via Paper Data Collection Tool

- Email transmission of the electronic SAE Form (paper data collection tool) is the preferred method to transmit this information to the Medical Monitor or study CRA. A scanned copy of a printed SAE form may be accepted if the electronic form cannot be submitted.
- In rare circumstances and in the absence of email equipment, notification by telephone is acceptable with a copy of the SAE Form sent by overnight mail or courier service.

- Initial notification via telephone does not replace the need for the investigator to complete and sign the SAE Form within the designated reporting timeframes.
- Contacts for SAE reporting can be found on the title page of this document (the Medical Monitor) or in the sponsor contact list provided separately.

8.7.8 Regulatory Reporting Requirements for SAEs

- Prompt notification by the investigator (within 24 hours of becoming aware of the event) to the sponsor of an SAE is essential so that legal obligations and ethical responsibilities towards the safety of participants and the safety of a study intervention under clinical investigation are met.
- The sponsor has a legal responsibility to notify both the local regulatory authority and other regulatory agencies about the safety of a study intervention under clinical investigation. The sponsor will comply with country-specific regulatory requirements relating to safety reporting to the regulatory authorities, institutional review boards (IRBs)/independent ethics committees (IECs), and investigators.
- An investigator who receives an investigator safety report describing an SAE or other specific safety information (e.g., summary or listing of SAEs) from the sponsor will review and then file it along with the IB and will notify the IRB/IEC, if appropriate according to local requirements.

8.7.9 Pregnancy

- If a pregnancy is reported, the investigator will record pregnancy information on the appropriate form and submit it to the sponsor within 24 hours of learning of the pregnancy.
- While pregnancy itself is not considered to be an AE or SAE, any pregnancy complication or elective termination of a pregnancy for medical reasons will be reported as an AE or SAE.
- Abnormal pregnancy outcomes (e.g., spontaneous abortion, fetal death, stillbirth, congenital anomalies, ectopic pregnancy) are considered SAEs and will be reported as such.
- The participant will be followed to determine the outcome of the pregnancy. The investigator will collect follow-up information on the participant and the neonate and the information will be forwarded to the sponsor.
- Any poststudy pregnancy-related SAE considered reasonably related to the study intervention by the investigator will be reported to the sponsor as described in [Section 8.7.8 Regulatory Reporting Requirements for SAEs](#). While the investigator is not obligated to actively seek this information in former study participants, they may learn of an SAE through spontaneous reporting.

Any PABP who becomes pregnant while participating in the study will be withdrawn from the study and followed up for safety as stated above.

8.7.10 Disease-related Events and/or Disease-related Outcomes

This healthy volunteer study does not define any disease-related events.

8.7.11 Interruptions and Arrangements Due to COVID-19 Pandemic or Any Other Unforeseen Emergency at Clinic Locations

This clinical study may be impacted by the Coronavirus Disease 2019 (COVID-19) global pandemic. Special arrangements may be required for study continuation and participant and study site staff safety due to this or any other unforeseen emergency in the future. The following accommodations in the protocol will be allowed, captured, and noted in the Clinical Study Report as COVID-19 deviations when applicable:

- Delaying the start of the first inpatient arm after enrollment
- Delaying the second inpatient assessment window

For any participant with COVID-19 related illness, continued study participation after full recovery of the disease may be appropriate after discussion between the site physicians and Medical Monitors on a case-by-case basis.

8.8 Other Assessments

8.8.1 Pharmacokinetics

PK parameters are collected in this study as a Primary Outcome measure as per [Section 8.5.1.1 PK Blood Sampling](#).

8.8.2 Genetics

This study may perform a Cytochrome P450 Genotyping Panel to assess variants in genes that code CYP isozymes that may influence pharmacokinetics and may predict or explain non-standard dose requirements, therapeutic failure, or adverse reactions.

8.8.3 Biomarkers

Biomarkers are not evaluated in this study.

8.8.4 Immunogenicity Assessments

Immunogenicity is not evaluated in this study.

8.8.5 Medical Resource Utilization and Health Economics

Medical resource utilization and health economics parameters are not evaluated in this study.

9.0 Statistical Considerations

The statistical analysis plan (SAP) will be finalized prior to database lock and includes a more technical and detailed description of the statistical analyses described in this section. This section is a summary of the planned statistical analyses of the most important endpoints including primary and safety endpoints.

9.1 Statistical Hypotheses

The primary objective is to analyze change in exposure measurements in participants with and without food. Thus, the null hypothesis to be tested is that food will have no effect on exposure of MDMA.

9.1.1 Multiplicity Adjustment

No adjustments are planned for controlling overall type I error as it is not relevant for this type of study.

9.2 Analysis Sets

For the purposes of analysis, the following analysis sets are defined:

Participant Analysis Set	Description
Full analysis set (FAS)	All randomized participants. Participants will be included in the analyses according to the intervention they actually received.
Safety analysis set	All participants who are exposed to IMP. Participants will be included in the analyses according to the intervention they actually received.
PK analysis set	All participant who have sufficient timepoints for evaluable PK and do not vomit within 4 hours of dosing.

